Clinical Phase:	Medical Device Study Risk category A, Phase of development I
Background and Rationale:	
Mental disorders are highly prevalent, undertreated, and associated with substantial disability and reduced quality of life (Demyttenaere et al., 2004). One third of patients with mental disorders comorbidly suffer from insomnia disorder according to the Diagnostic and Statistical Manual of Mental Disorders (American Psychiatric Association, 2013, S. 5). Following current European and American practice guidelines for adult patients, cognitive behavioral therapy for insomnia (CBT-I) is the first line treatment (Qaseem et al., 2016; Riemann et al., 2017). Various adaptations of CBT-I for different target groups and settings have been developed. One of them is Brief Behavioral Treatment for Insomnia (BBT-I), consisting of four sessions centering of bedtime restriction (Troxel et al., 2012). This demonstrates that brief versions of CBT-I can be similarly effective as the complete program. The intervention "SleepExpert" is based on BBT-I as a brief version of CBT-I, the first-line treatment for insomnia according to current guidelines. There has been a feasibility study, however this study was uncontrolled. In the proposed project, we aim to compare treatment as usual (TAU) plus SleepExpert to TAU plus sleep monitoring in a pilot randomized controlled trial. The objective is to target sleep to improve mental health and to investigate the efficacy of SleepExpert for the improvement of sleep and mental health.

Objective(s):	
The primary objective is to assess whether there is a significantly greater reduction in self-assessed insomnia severity (as measured by the Insomnia Severity Index, ISI) across six months (interaction effect Group and Timepoint) in patients in the Tau plus SleepExpert group, compared to patients in the TAU plus sleep monitoring group.
 
The secondary objective is to assess whether there is a significantly greater improvement in general mental health (Brief Symptom Inventory) across six months (interaction effect Group and Timepoint) in patients in the TAU plus SleepExpert group, compared to patients in the TAU plus sleep monitoring group.

Outcome(s):	The primary outcome will be insomnia severity measured with the Insomnia Severity Index (ISI) (Bastien et al., 2001). The ISI will be administered before the intervention (T0) and one, two, 12, and 26 weeks after the start of the intervention
Study design:	This project is a prospective randomized controlled clinical pilot trial with a cluster-crossover design involving two groups: An interventional group (TAU, plus SleepExpert) and a control group (TAU plus sleep monitoring).

Inclusion / Exclusion criteria:	
Inclusion criteria:
 
 - Age 18 years or older - Documented diagnosis of acute insomnia, i.e. insomnia criteria according to ICD-10 for at least 2 weeks (Ellis, Gehrman, Espie, Riemann, & Perlis, 2012) - Insomnia Severity Index (ISI) total score > 7, equivalent to relevant insomnia (Gagnon, Bélanger, Ivers, & Morin, 2013) - Inpatient in one of the two participating psychiatric wards in the UPD Bern - Ability to understand the aims and procedures of the study - Willingness to participate and ability to provide written informed consent 
Exclusion criteria:
 
 - Incapability of judgement - Inability to participate in a low-threshold behavioral treatment program, e.g. due to severe cognitive impairment or high symptom severity precluding participation (e.g., severe catatonic symptoms, massive hallucinations, acute endangerment to self or others, involuntary commitment). Note that the named symptoms will lead to exclusion only if they lead to inability to give informed consent or an inability to participate in the program. Excluded patients will be re-assessed regularly and included if symptoms improve and participation is possible at a later point in time.
Measurements and procedures:	
Patients will first be screened and assessed for eligibility. Eligible patients who signed the informed consent form will undergo a first assessment (T0) and then participate in the intervention. Additional assessments will be made one, two, 12, and 26 weeks after the start of the intervention.

Study Product / Intervention:	
TAU plus "SleepExpert" behavioral treatment program for insomnia (face-to-face combined with a web application)

Control Intervention (if applicable):	
Treatment as Usual (TAU) plus sleep monitoring

Number of Participants with Rationale:	
Assuming an alpha error level of 0.05 (two-sided) and a power of 0.8, a total sample size of n=60 will be sufficient to detect a medium effect (Cohen's d=0.65). This is a pilot trial with the primary aim of collecting qualitative experience and preliminary efficacy data.

Study Duration:	
Two years

Study Schedule:	
Month Year of First-Participant-In (planned): August 2021 Month Year of Last-Participant-Out (planned): January 2024

Investigator(s):	
[name]. [name] (Sponsor-Investogator) Institution: UPD Bern Position: Chefarzt, Stv. Ärztlicher Direktor Address: [name] Mail: [contact]
 
Dr. phil. [name] (Sub-Investigator) Institution: UPD Bern Position: Psychologist Address: [name] Mail: [contact]

Study Centre(s):	
Single-centre Universitäre Psychiatrische Dienste Bern

Statistical Considerations:	
Our primary analysis will be a linear mixed model with the following co-variables: fixed intervention effect (TAU plus SleepExpert versus TAU plus sleep monitoring), fixed baseline ISI score effect, random patient effect (multiple ISI scores during follow-up), random cluster effect. Depending on model fit, we may need to simplify the model.

GCP Statement:	
This study will be conducted in compliance with the protocol, the current version of the Declaration of Helsinki, the ISO EN 14155 norm as well as all national legal and regulatory requirements.

ABBREVIATIONS

AE	Adverse Event
ASR	Annual Safety Report
BASEC	Business Administration System for Ethical Committees, (https://submissions.swissethics.ch/en/)
CA	Competent Authority (e.g. Swissmedic)
CEC	Competent Ethics Committee
CRF	Case Report Form
ClinO	Ordinance on Clinical Trials in Human Research (in German: KlinV, in French: OClin, in Italian: OSRUm)
eCRF	Electronic Case Report Form
CTCAE	Common terminology criteria for adverse events
DSUR	Development safety update report
GCP	Good Clinical Practice
IB	Investigator's Brochure
Ho	Null hypothesis
H1	Alternative hypothesis
HRA	Federal Act on Research involving Human Beings (in German: HFG, in French: LRH, in Italian: LRUm)
IMP	Investigational Medicinal Product
IIT	Investigator-initiated Trial
ICH	International Council for Harmonisation of Technical Requirements for Pharmaceuticals for Human use
ISO	International Organisation for Standardisation
ITT	Intention to treat
MD	Medical Device
MedDO	Medical Device Ordinance (in German: MepV, in French: ODim)
PI	Principal Investigator
SAE	Serious Adverse Event
SDV	Source Data Verification
SOP	Standard Operating Procedure
SPC	Summary of product characteristics
SUSAR	Suspected Unexpected Serious Adverse Reaction
TMF	Trial Master File

1. STUDY ADMINISTRATIVE STRUCTURE

1.1 Study Plan

Table 1. Patient schedule

	screening	T0	T1 (week1)	T2 (week2)	T3 (week12)	T4 (week 26)	debriefing***
Time point (days)	at or after admission to ward until T 0	0	7±2	14±2	84±7	182±7	
Eligibility screen	x						
Informed consent	x (signature 24 hours or more after first information)						
Medical History	x						
Insomnia Severity Index	x	x	x	x	x	x	
Brief Symptom Inventory		x		x		x	
Beck Depression Inventory		x		x		x	
Visual analogue scales*		x	x	x	x	x	
Daily sleep Diary**			x	x	x	x	
Medication status	x	x	x	x	x	x	
TAU plus SleepExpert							
TAU plus sleep monitoring***							
Adverse Events		x	x	x	x	x	

* self-constructed visual analogue scales will be used to measure subjective sleep quality, mood, concentration, and tiredness

** the sleep diary will be used continuously throughout the study period (baseline until T4)

*** debriefing: All patients, i.e. the TAU plus sleep monitoring and TAU plus SleepExpert group will have an individual appointment with a sleep expert (physician or psychologist) after completion of the study, i.e. after 6 months, in which the gathered information (sleep diaries and actigraphy data) will be discussed and individualized further diagnostics and treatments, if needed, will be initiated.

1.5 Laboratory

Not applicable

1.7 Data Safety Monitoring Committee

A DSMC is not needed because the study doesn't come along with great risks.

1.8 Any other relevant Committee, Person, Organisation, Institution

Not applicable.

2. ETHICAL AND REGULATORY ASPECTS

The decision of the CEC concerning the conduct of the study will be made in writing to the Sponsor-Investigator before commencement of this study. The clinical study can only begin once approval from all required authorities has been received. Any additional requirements imposed by the authorities shall be implemented.

2.1 Study registration

Intended registry: clinicaltrials.gov & Swiss National Clinical Trial Portal

2.2 Categorisation of study

The psychotherapeutic protocol used in this study (Cognitive Behavioral Therapy for Insomnia) is non-invasive. Comparable therapeutic protocols have been thoroughly investigated in patients with insomnia without adverse events. Sleep restriction as used in this therapy may be associated with temporary daytime sleepiness. No long-lasting or serious adverse effects of these psychotherapies are known. In addition, multiple previous studies have shown that Cognitive Behavioral Therapy for insomnia is also feasible as an online application. The new aspect of this study is a change of the target group: instead of patients with insomnia only, the intervention will be applied in patients with insomnia and mental disorders (both disorder groups are category F in the ICD-10). We have no reason to assume that the psychotherapeutic protocol is associated with unexpected risks in this target group. The internet-based self-help program platform developed by [name], University of Bern, that will be used in this study has received a CE mark in 2018 that is valid for 5 years. All examinations and interventions in this study are in accordance with current safety standards and the risk associated with a participation in this study is regarded as minimal. Thus, this study belongs to category A.

2.3 Competent Ethics Committee (CEC)

The Sponsor-Investigator ensures that approval from an appropriately constituted Competent Ethics Committee (CEC; Kantonale Ethikkommission (KEK) Bern) is sought for the clinical study.

The Sponsor-Investigator further ensures that no changes will be made to the protocol or in research activities without his prior approval and, in case of significant changes according to ClinO Art.29, CEC approval. Exempt from this requirement are measures, which have to be taken immediately in order to protect the study participants. Any safety or protective measures that have to be taken during the conduct of the clinical trial due to unanticipated risks to humans will be reported to the CEC within 7 days. Amendments will be reported according to section 2.10 and intermediary reports (annual safety reports) will be forwarded to the CECs yearly.

Premature study end or interruption of the study will be reported within 15 days. The regular end of the study will be reported to the CECs within 90 days and the final study report shall be submitted within one year after study end.

2.4 Competent Authorities (CA)

Approval from Swissmedics is not necessary because this is a category A study.

2.5 Ethical Conduct of the Study

The study will be carried out in accordance to the protocol and with principles enunciated in the current version of the Declaration of Helsinki, the European Regulation on medical devices 2017/745 and the ISO Norm 14155 and ISO 14971, the Swiss Law and Swiss regulatory authority's requirements. The CEC and regulatory authorities will receive annual safety and interim reports and be informed about study stop/end in agreement with local requirements.

2.6 Declaration of interest

The investigators of this study have no intellectual, financial, proprietary or other conflict of interest related to the proposed study.

2.7 Patient Information and Informed Consent

The investigators will explain the following to each potential participant:

- The nature of the study, its purpose, the procedures involved, the expected duration, the potential risks and benefits and any discomfort it may entail
- That participation in the study is voluntary and that he/she may withdraw from the study at any time
- That withdrawal of consent only will terminate study related treatment and investigations, but not affect subsequent medical assistance and treatment
- That the participant's medical records may be examined by authorised individuals other than their treating physician

During the informed consent procedure, the candidate will have the opportunity to ask questions concerning the study and he or she will receive a patient information sheet and a consent form describing the study. The patient information sheet will provide all the information necessary for the candidate to make an informed decision about study participation.

The candidate should read and consider the patient information and be given at least 24 hours to consider study participation.

When willing to take part in the study, the candidate will sign and date the informed consent form. The investigator having discussed the study with the participant must also sign and date the form. The signed form will be retained as part of the study records, and a copy will be given to the participant.

The formal consent of a participant, using the approved consent form, will be obtained before the participant is submitted to any study specific procedure.

Asymmetric information of patients on wards randomized to the control- vs. intervention-arm will be performed because patients in the control-arm have no opportunity to receive the treatment and thus information about SleepExpert may be demotivating. All patients, including those in the control arm, will receive treatment as usual, i.e. psychiatric treatment following the current standard clinical practice according to clinical guidelines. Whether or not SleepExpert has an additional benefit is the research question of the proposed trial, but is not yet clear. Thus, it is ethical to not give SleepExpert to the patients in the control arm and to not inform them about the intervention.

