6. STUDY DESIGN

6.1 General study design and justification of design

This project is a prospective randomized controlled clinical pilot trial with a cluster-crossover design

involving two groups: An interventional group (TAU, plus SleepExpert) and a control group (TAU plus sleep monitoring).

Two different wards in the trial site (UPD Bern) will constitute the clusters. The study is conceptualized with a crossover, i.e. clusters (wards) will first be randomized to one of the groups for a duration of 4 months. After a washout-phase of two months, they will then be allocated to the other group for another 4 months. The order (TAU plus SleepExpert first vs. TAU plus sleep monitoring first) will be randomly allocated in a 1:1 fashion.

A total of 60 patients will be included. Patients will be assessed before the intervention (T0) and at the following time-points after the start of the intervention: 1 week (T1), 2 weeks (T2), 12 weeks (T3) and 26 weeks (T4).

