7.2 Recruitment and screening

During the enrolment phase, all patients admitted to the participating wards of the UPD Bern will be screened in person. The screening will consist of a few questions regarding sleep, implemented into the routine clinical interview at enrolment, and filling in the insomnia severity index (Gagnon et al., 2013). The clinical interview as well as the questionnaire (insomnia severity index) are part of the clinical routine in our hospital and not specific for this study. Eligible patients will be contacted by study staff, informed about the study, and invited to participate. For further information about the study a flyer containing the most important details will be given to the participants. The screening and enrolment process will be standardized across the wards to minimize the risk of selection bias.

Each patient in the clinic fills in a general consent form at admission, stating whether or not they agree to be approached for information about ongoing studies. Only patients who gave their written general consent will be contacted. There will be two different study information documents with attached consent forms, one for the active study phase where TAU plus SleepExpert is running, and one for the control phase where TAU plus sleep monitoring is running. Since patients are not randomized on an individual basis, but clusters (wards) are randomized, patients who are screened for the project in a phase where TAU plus sleep monitoring is running on their ward cannot be randomized to TAU plus SleepExpert. In these phases, it may be demotivating for patients to be informed about the SleepExpert treatment, because it is not available for them. Thus, we decided to give them extensive relevant information about the project they can participate in (sleep monitoring) and only basic information about the use of their data within a clinical trial.

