7.3 Assignment to study groups

The two clusters (UPD wards) will be assigned to one of the following two study sequences – while one cluster will follow the first sequence, the other one will follow the second sequence. Which ward will follow which study sequence will be randomly assigned.

- TAU plus SleepExpert first for 4 months; fade-out for one month; wash-out for one month; TAU plus sleep monitoring for 4 months
- TAU plus sleep monitoring for 4 months; fade-out for one month, wash-out for one month; TAU plus SleepExpert for 4 months

During the TAU plus SleepExpert and TAU plus sleep monitoring phases, patients will be actively recruited. During the fade-out phases, no active recruitment will take place, but already recruited patients will be able to complete their treatment. During the wash-out phase, no recruitment and no study-related treatment will take place.

Depending at which stage of the study the ward stands at the time point when a subject is admitted to the ward, her or she will either receive TAU plus SleepExpert or TAU plus sleep monitoring, or, if admitted during the wash-out phase, the subject will not be able to participate in the trial.

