11.2 Determination of Sample Size

A power analysis was conducted with G-Power (Faul, Erdfelder, Lang, & Buchner, 2007). Assuming an alpha error level of 0.05 (two-sided) and a power of 0.8, a total sample size of n=60 will be sufficient to detect a medium effect (Cohen's d=0.65). This is a pilot trial with the primary aim of collecting qualitative experience and preliminary efficacy data. A large confirmatory trial will be conducted if the results of this pilot trial are encouraging.

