11.4.2 Primary Analysis

The primary outcome, i.e. the four overall scores of the ISI of all follow-up time-points will be analyzed with a mixed effects linear model. The model will take into account the hierarchical structure of the data: multiple ISI scores per patient and clusters (cross-over). Because of the complexity of the data and the small number of clusters we assume that we will not be able to introduce random effects for patients and clusters. However, our first approach will still be a linear mixed model with the following co-variables: fixed intervention effect (TAU plus SleepExpert versus TAU plus sleep monitoring), fixed baseline ISI score effect, random patient effect (multiple ISI scores during follow-up), random cluster effect. Depending on model fit, we may need to simplify the model and modify the random effects. This model is pre-specified and the rationale for switching will be made explicit. The analysis will be made after all data has been collected by one of the principal investigators.

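### Patients consent after the ward's arm is fixed and on an arm-specific information sheet, so those who enrol can differ by arm, while the primary model adjusts only for baseline ISI

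*Combined protocol and SAP*

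**What the plan says.** **Allocation comes before consent.** Sections 6.1 and 7.3 of the combined protocol and SAP randomise the order in which two wards deliver the two conditions. A patient's arm is set on admission: "Depending at which stage of the study the ward stands at the time point when a subject is admitted to the ward". Section 7.2 confirms that someone screened in a control phase cannot be allocated to SleepExpert. Section 6.3 says that care providers on the wards always know who received it.

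**The offer differs by arm.** Section 2.7 states: "Asymmetric information of patients on wards randomized to the control- vs. intervention-arm will be performed". Sections 6.2.2 and 7.2 describe two information sheets with their own consent forms. Control patients learn about sleep monitoring but not about SleepExpert. The stated reason is that hearing of an unavailable treatment could demotivate them.

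**Stated safeguards.** Sections 7.2 and 9.3.1 have every admission to the wards screened. Section 7.2 adds: "The screening and enrolment process will be standardized across the wards to minimize the risk of selection bias". Section 6.1 has each ward deliver both conditions in turn.

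**Analysis.** The primary model in 11.4.2 contains the intervention effect, a "fixed baseline ISI score effect", and random patient and cluster effects that may have to be simplified. It names no other patient-level covariate. Section 11.4 defers details to an SAP to be written at the start of recruitment.

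**The concern.** In an individually randomised trial, consent precedes allocation, so the choice to take part cannot depend on the arm. Here it can. One group decides about a treatment for insomnia and the other about a diary app. The protocol's own reasoning accepts that what is offered affects willingness: section 2.7 withholds information to avoid demotivating control patients, and section 3.6 rejects a dummy treatment partly because it would lower motivation to participate.

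Eligibility is exposed in a smaller way. Section 7.1 excludes patients unable to take part in a behavioural programme, and section 3.8 mentions ability to join a group session. Only the SleepExpert arm has that session (8.1.1, 8.1.2), so in control phases the judgement is hypothetical.

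If those who consent differ in prognosis beyond what T0 ISI captures, the difference enters the treatment estimate. It could create an apparent effect or conceal a real one. Section 11.2 makes the confirmatory trial depend on encouraging pilot results, so either error has consequences.

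**Working it through.** **1. The plan's own figure.** Section 11.2 gives "Assuming an alpha error level of 0.05 (two-sided) and a power of 0.8", d = 0.65 and 60 patients in total. A two-sided two-sample t-test at those values needs 38.1, so 39, per arm (78 in total). With 30 per arm its power is 0.70. The figure of 60 reproduces only one-sided (power 0.80 at 30 per arm). That is a separate matter; it enters here only as the no-bias reference of 0.70.

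**2. Does any safeguard act on the consent step?**

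| Safeguard | What it controls | What it leaves open |
|---|---|---|
| All admissions screened (7.2, 9.3.1) | Who is considered | Who accepts |
| Standardisation across wards (7.2) | Differences between wards in procedure | The sheet still differs between phases, and phase is the arm |
| Ward crossover (6.1) | Stable ward differences | Each patient is in one phase, so differential consent within a ward remains |
| Random cluster effect (11.4.2) | Ward level | Patient mix; the term may also be dropped |
| Blinded assessors and analysts (6.2.2) | Assessment and analysis | Consent, where the sheet itself reveals the condition |
| Baseline ISI (11.4.2) | Insomnia severity at T0 | General severity, sleep medication, motivation |

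None acts on who accepts the offer.

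**3. Illustrative size.** Inputs: 60 patients (6.1), taken as 30 per arm (equal split assumed); two-sided alpha 0.05; d = 0.65. The residual imbalance b, in SD of the outcome after allowing for baseline ISI, is assumed, because the documents give no value.

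- Non-centrality = b × √(30/2) = b × 3.873, with 58 degrees of freedom and critical value 2.002.
- False-positive rate = P(|T| > 2.002) under that non-central t.
- If b runs against SleepExpert, power is that of a t-test at effect 0.65 − b.

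| b (SD, assumed) | b / 0.65 | False-positive rate, no true effect | Power at d = 0.65 if b runs against SleepExpert |
|---|---|---|---|
| 0 | 0% | 5.0% | 0.70 |
| 0.05 | 8% | 5.4% | 0.63 |
| 0.10 | 15% | 6.7% | 0.55 |
| 0.20 | 31% | 11.9% | 0.40 |
| 0.30 | 46% | 20.8% | 0.27 |

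**4. What such values of b would require.** For one unadjusted binary factor, b = (difference in its prevalence between arms) × (its effect on outcome in SD, given baseline ISI). Assumed differences of 10 to 30 percentage points and effects of 0.3 to 0.8 SD give b from 0.1 × 0.3 = 0.03 to 0.3 × 0.8 = 0.24, with false-positive rates of 5.2% to 15.0%. Reaching b = 0.30 through a single factor with an effect of 0.8 SD needs a difference of 0.30 / 0.8 = 37.5 points. The last row of the table is therefore a high case.

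The calculation ignores clustering and repeated measures. It shows scale and is not a prediction for the planned mixed model.

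**The case against.** The strongest reply is that the sponsor saw the risk and disclosed it. The two sheets are described openly and with a reason, all admissions are screened, and 7.2 gives minimising selection bias as a purpose; it does not say that the bias is eliminated. This is also a pilot, with qualitative experience and preliminary efficacy data as its stated aim, so a false-positive argument weighs less than in a confirmatory trial. These points stand. They lower the weight of the concern without closing the route by which the arms can come to differ.

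A reader might infer that any imbalance would go unseen. The documents do not support that. BSI, BDI, visual analogue scales and medication status are collected at T0 in both arms (Table 1, 9.3.2), so imbalance on those measures would be visible, and the SAP is still to come. What these documents lack is a pre-specified adjustment beyond ISI and a plan to report consent by phase.

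A reader might also infer that the bias must favour SleepExpert or must be large. Neither follows. If the treatment offer drew patients with a worse outlook, it would mask an effect, and no figure in the documents fixes the size.

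Finally, one might want main diagnosis in the model. It is not a listed T0 item; Table 1 has only medical history at screening. Section 9.2.2 expects several, often comorbid, diagnoses. With four or five groups it would use three or four degrees of freedom by itself.

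**Conclusion.** The concern holds in a limited form. The arm is fixed before consent, the information sheet and consent form differ by arm, and the safeguards do not act on who accepts. The primary model adjusts for no patient characteristic except baseline ISI. The arms can therefore enrol different patients; the documents do not show that they will.

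Direction and size cannot be derived. Under the assumptions stated (30 per arm, simple t-test, residual imbalance of 0.05 to 0.3 SD), the two-sided false-positive rate is about 5% to 21%. The same imbalance in the opposite direction lowers power at d = 0.65 from 0.70 to between 0.63 and 0.27. This is worth correcting in the SAP and does not call for a change of design.

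**What to change.** Keep both information sheets.

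1. **Section 11.4.2 and the SAP.** Pre-specify T0 BSI total and T0 sleep-medication use (yes/no, derived from the medication status recorded at T0) as fixed covariates next to T0 ISI. Report the ISI-only model as a sensitivity analysis. Do not require main diagnostic group. Cost: about two degrees of freedom with 60 patients and no new assessments. Limit: neither covariate measures motivation, so some selection may remain.
2. **Recruitment reporting.** Keep aggregate counts of patients screened, with ISI above 7, approached and consented, by ward and phase. Report these with T0 characteristics by arm. Cost: a simple log, since the ISI is already routine at admission. Report screening ISI of patients who do not consent only if the consent basis allows it; the general consent described in 7.2 concerns being approached about studies and does not mention research use of such scores.
3. **Section 7.2.** Add that standardised screening does not remove selection through arm-specific consent. Cost: one sentence.
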